Appendix E6: Subgroup analysis for primary outcome

Example Table for subgroup analysis

Subgroup description	E-MOTIVE		Control		Adjusted summary measure and 95% CI	p-value for interaction	Ratio of ratios
	Baseline period (N =)	Post-randomisationperiod (N =)	Baseline period (N =)	Post-randomisationperiod (N =)			
Kenya							
Nigeria							
...	

Appendix E7: Template report

A template report for the final analyses will be provided in a separate document.

Appendix Table E8: *Estimates of the power with changes to key design parameters.*

			RR = 20%			RR = 25%			RR = 30%			
			Control Prevalence									
			1.50%	2.00%	4.00%	1.50%	2.00%	4.00%	1.50%	2.00%	4.00%	
CAC = 0.95	ICC	0.001	86.8	94.5	99.9	97.4	99.5	99.9	99.7	99.9	99.9	
		0.02	43.2	54.4	84	62	74.6	96.3	78.8	89.1	99.5	
		0.05	24.8	31.6	56.1	36.8	46.7	76.4	50.6	62.7	90.3	
CAC = 0.97		0.001	87.5	95	99.9	97.6	99.5	99.9	99.8	99.9	99.9	
		0.02	53.9	66.3	92.5	74.1	85.5	99.1	88.8	95.7	99.9	
		0.05	34.1	43.4	72.7	50.2	62.4	90.1	66.8	79.1	97.7	
CAC = 1.00		0.001	89.7	96.2	99.9	98.3	99.7	99.9	99.9	99.9	99.9	
		0.02	83.7	92.1	99.9	95.9	99	99.9	99.5	99.9	99.9	
		0.05	83	92.6	99.9	96.2	99.1	99.9	99.4	99.9	99.9	

Note: Power has been calculated assuming 72 health facilities, with an average number of 192 births per month (14-month study), and a coefficient of variation of cluster sizes of 0.5. CAC: Cluster autocorrelation; ICC: Intra cluster correlation. RR = Risk reduction

Appendix E9: Estimand Information

Estimand aspect	Definition for different outcomes and analysis populations					
	Primary composite outcome (total population)	Key implementation outcomes (target population)	Binary secondary clinical and implementation outcomes (total population)	Continuous secondary outcomes (total population)	Binary secondary implementation outcomes (target population)	
Population						
Health Facilities	Health facilities that have 1000 to 5000 births a year and provide comprehensive obstetric care with ability to perform surgery for PPH.					
Research Participant	All healthcare providers attending vaginal births at the study facilities.					
Patient	All women having a verified vaginal birth in the study facilities					
Treatment conditions	E-MOTIVE vs. standard care					
Endpoint	Composite of three clinical outcomes (see section 4.5) measured until discharge from the health facility	Classification according to outcome at discharge from the health facility	Outcome on continuous measure at discharge from the health facility	Classification according to outcome at discharge from the health facility	Classification according to outcome at discharge from the health facility	
Population-level summary measure	Relative Risk and Risk Difference	Relative Risk and Risk Difference	Relative Risk and Risk Difference	Mean difference.	Relative Risk and Risk Difference	
Participant- or cluster-average effect	Participant-average.					
Marginal or conditional effect	Conditional					
Handling intercurrent events	Cluster-level intervention and implementation. Patients cannot prematurely stop treatment. Additional treatments are captured as secondary implementation outcomes. Any harm is captured as secondary clinical outcomes. Patients are followed up to discharge from health facility (or died whilst in the facility). Primary					

	outcome data can be missing if blood loss data is not source verified or if a case report form is not complete. A sensitivity analysis will evaluate including missing data in the analysis.
--	--

References

1. Hemming, K., et al., *Interim data monitoring in cluster randomised trials: practical issues and a case study*. Clinical Trials, 2021. **18**(5): p. 552-561.
2. Pocock, S.J. and R. Simon, *Sequential treatment assignment with balancing for prognostic factors in the controlled clinical trial*. Biometrics, 1975: p. 103-115.

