7.1. Estimands

Since E-MOTIVE is a cluster trial, the summary measure of the effect of E-MOTIVE can be measured in different ways. That is to say, the unit of inference of whether the treatment is beneficial can be made at the unit of randomisation (cluster) or at the unit of data collection (participant). Please see Appendix E8 for further information.

In E-MOTIVE, for all outcomes (both clinical and implementation), we will be estimating the participant-average summary measure. This will indicate the average summary measure across patients, that is, how effective E-MOTIVE is for the average participant. See sections 7.4 for details on the analysis methods.

The list of clinical outcomes and implementation outcomes is given in section 4.6.

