7.4. Primary outcome analysis

The model being fitted to the binary primary composite outcome will be a mixed-effect logistic regression model with robust standard errors.

To account for clustering, random effects (for cluster and cluster-period) are included (see section 7.4.1). We will account for the time-period using fixed-effects (see section 7.4.2), and will adjust for covariates used in the randomisation in the first instance (see section 7.4.3). If there are issues with model-convergence, then a plan is in place (see section 7.4.4).

Risk ratios and risk differences will then be derived using marginal standardisation [10], as in for example a CRT by Kirkwood et al [11]. Under this approach, the mean risk under the control condition and intervention condition is obtained. The risk ratio is then derived using the mean risk in intervention condition and by the mean risk in the control condition, with the calculation

being performed on the log scale. The risk difference is derived as the mean risk in intervention condition minus the mean risk in the control condition. We will use the unconditional standard errors to obtain the confidence interval, as this allows for correlation amongst the observations [12].

A small sample correction will not be included in the main analyses as the number of clusters is expected to be sufficiently large to maintain the type I error rate [13].

The integration method used will be mean-variance adaptive Gauss-Hermite quadrature, which is the default in Stata.

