7.4.4. Primary outcome - model non-convergence

If the mixed-effect logistic regression model with random cluster and cluster-period effects does not converge, we will remove the cluster-period random effects and fit a mixed-effects model with a random effect for cluster.

If this model does not converge, then we will perform a cluster-level analysis weighted by cluster size to ensure we are targeting the participant-level effect [9]. To perform a cluster-level analysis, for each outcome and for each cluster we will calculate a cluster-level summary statistic for the baseline period and for the post-randomisation period separately. The cluster-level summary statistic will be the proportion of the cluster who experience the outcome.

The data will then be transformed from long format to wide format. That is, instead of having two observations per cluster (one observation that describes the summary statistic during the baseline period and one observation that describes the summary statistics during the post-randomisation phase), each cluster will have one row of data.

Relative risk

To obtain a relative risk, we will fit a linear regression model to a transformed cluster-level summary statistic (log transformation) with a fixed effect for allocated exposure to E-MOTIVE and a fixed-effect for baseline summary measure. We will take the exponential of the covariate related to allocated exposure to E-MOTIVE to obtain the relative risk and 95% confidence intervals. We will use the unconditional standard errors to obtain the confidence interval, as this allows for correlation amongst the observations [12].

Risk difference

To obtain the risk difference, a linear regression model will be fitted to the cluster-level proportions with a fixed-effect for allocated exposure to E-MOTIVE and a fixed-effect for baseline summary measure. We will use the unconditional standard errors to obtain the confidence interval, as this allows for correlation amongst the observations [12].

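### SAP 7.4.4 says size weighting makes the primary-outcome fallback target the participant-level effect, but its risk ratio is a ratio of geometric means and in general is not that quantity

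*SAP*

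**What the plan says.** SAP 7.1 states that for all outcomes "we will be estimating the participant-average summary measure". The estimand table in SAP Appendix E9 repeats this as "Participant-average", with "Relative Risk and Risk Difference" as the summary measures for binary outcomes.

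In SAP 7.4 the main analysis fits a mixed logistic model and then standardises: "the mean risk under the control condition and intervention condition is obtained", and the risk ratio and risk difference are built from those two means.

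SAP 7.4.4 covers non-convergence. If the model with cluster and cluster-period effects fails, and the model with a cluster effect alone also fails, the plan moves to a "cluster-level analysis weighted by cluster size to ensure we are targeting the participant-level effect". Two regressions follow, each adjusted for the baseline summary. The risk difference comes from a linear model for the untransformed facility proportions. The risk ratio comes from a linear model for their logarithms: "We will take the exponential of the covariate related to allocated exposure to E-MOTIVE to obtain the relative risk".

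The SAP does not say that the log transformation changes the target, and it gives no back-correction.

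**The concern.** Weighting decides how much each facility counts. It does not undo the logarithm taken before averaging. A size-weighted mean of log proportions, once exponentiated, is a geometric mean, and a ratio of geometric means is not in general the ratio of mean risks across patients.

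Section 7.4.4 would therefore produce a risk ratio and a risk difference that answer different questions, under a sentence saying that the weights put both on target. If this branch became the primary result, its risk ratio would also sit beside sensitivity analyses in SAP 7.11 that use marginal standardisation or a log-link GEE, both of which compare mean risks. A discrepancy could then be misread as sensitivity to missing data or to cluster size.

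The SAP itself allows for the condition that creates the gap. Section 7.2 considers it plausible that cluster size is informative, and lists differing effects in small and large clusters as one way this can arise. Section 7.10 plans subgroup analyses by baseline PPH rate, facility size, country and facility compliance.

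**Working it through.** **Inputs from the SAP.** 78 facilities allocated 1:1, so 39 per arm (4.3). 192 births per month × 7 months = 1,344 per facility-period (4.7). Prevalence 3.6%, ICC 0.018 and CAC 0.97 (4.7). CV of cluster size 0.5 (note to Appendix Table E8). Target risk ratio 0.75 (25% reduction, 4.7).

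**Assumed.** How far the risk ratio varies between facilities, expressed as τ, the SD of the facility log RR. The documents give no value, so a range is shown. They also give no figure for the fallback's target, so there is none to reproduce.

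**Step 1: what each method estimates.** Let facility i have n_i births, risk p0_i under usual care and p1_i under E-MOTIVE.

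- Ratio of mean risks (7.4): R_A = Σ n_i p1_i / Σ n_i p0_i.
- Log-proportion fallback (7.4.4): R_G = exp(Σ n_i log p1_i / Σ n_i) / exp(Σ n_i log p0_i / Σ n_i).
- Risk-difference fallback (7.4.4): Σ n_i p1_i / Σ n_i − Σ n_i p0_i / Σ n_i, which uses arithmetic means and is on target.

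Under randomisation the baseline covariate changes precision, not these large-sample targets. If p1_i = R × p0_i in every facility, R_A = R_G = R.

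**Step 2: size of the gap.** Take log-normal facility risks, unrelated to size, with log-scale variances σ0² (usual care) and σ1² (E-MOTIVE). Each arithmetic mean is the geometric mean × exp(σ²/2), so

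R_G / R_A = exp{−(σ1² − σ0²)/2}.

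From the ICC, the CV of facility risks is √(0.018 × 0.964 / 0.036) = √0.482 = 0.694. Then σ0² = ln(1.482) = 0.393 and σ0 = 0.627.

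*Effects independent of baseline risk:* σ1² = σ0² + τ², so R_G / R_A = exp(−τ²/2). With R_A = 0.75:

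| τ | R_G / R_A | R_G |
|---|---|---|
| 0 | 1.000 | 0.750 |
| 0.1 | 0.995 | 0.746 |
| 0.2 | 0.980 | 0.735 |
| 0.3 | 0.956 | 0.717 |
| 0.5 | 0.882 | 0.662 |

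*Effects related to baseline risk:* let log RR change by g per unit of log baseline risk, so σ1 = (1 + g)σ0.

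- Larger benefit in high-rate facilities (g = −0.4, SD of log RR 0.4 × 0.627 = 0.25): σ1² = 0.36 × 0.393 = 0.142, ratio exp(0.126) = 1.134, R_G = 0.851.
- Larger benefit in low-rate facilities (g = +0.4, same SD): σ1² = 1.96 × 0.393 = 0.771, ratio exp(−0.189) = 0.828, R_G = 0.621.
- The two can cancel. With g = −0.1 plus independent variation of SD 0.273, σ1² = 0.81 × 0.393 + 0.075 = 0.393, so R_G = R_A = 0.75 although the SD of log RR is 0.28.

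**Step 3: behaviour in a trial of this size.** 3,000 simulated trials per row, true participant-average RR 0.75, effects independent of baseline risk. The fallback is fitted as in 7.4.4 with robust standard errors, and facilities with zero events are dropped because log(0) is undefined. The alternative is a log-link regression of event counts with log(births) as offset. Its baseline covariate is log((events + 0.5)/(births + 1)).

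| τ | 7.4.4 RR (coverage) | Log-link RR (coverage) |
|---|---|---|
| 0 | 0.745 (94.4%) | 0.749 (94.5%) |
| 0.1 | 0.742 (93.7%) | 0.750 (93.5%) |
| 0.2 | 0.730 (93.0%) | 0.748 (92.7%) |
| 0.3 | 0.714 (91.2%) | 0.750 (92.9%) |
| 0.5 | 0.655 (78.1%) | 0.743 (91.6%) |

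A second simulation gave 0.714 and 0.659 for the fallback at τ = 0.3 and 0.5, with coverage 90% and 79%. With RR 1.0 in low-rate and 0.6 in high-rate facilities, it gave 0.772 against a true 0.708. In that simulation the log-link model and the ratio of adjusted means from the risk-difference regression both stayed within about 0.01 of the truth.

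**The case against.** **The branch is remote.** It needs the single-random-intercept logistic model to fail as well. On planned figures each arm-period has 39 × 1,344 = 52,416 births, or about 1,887 events at 3.6%. Three usual-care cells plus one at RR 0.75 give about 3 × 1,887 + 1,415 = 7,076 events in 78 facilities. Nothing suggests that such a model would fail on those data. This stands, and it limits the importance of the point.

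**A cross-check is already planned.** The independence GEE in SAP 7.11, with log and identity links, compares size-weighted arithmetic mean risks. This stands in part: it is a sensitivity analysis, and the SAP notes its lower power.

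**The main model also drifts.** Section 7.4 fits one common log-odds effect. In a small simulation (200 trials per scenario, no covariates), with RR 1.0/0.6 the truth was 0.707, the 7.4 model gave 0.743 and the fallback 0.781. With independent SD 0.5 the three values were 0.750, 0.691 and 0.654. So part of the departure belongs to any common-effect model on a log-type scale. That narrows the contrast but does not make the sentence in 7.4.4 correct.

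**The estimand is loosely worded.** E9 does not define the risk ratio as a ratio of arithmetic means, and it also labels the effect conditional. The strict reading rests on 7.4. Even so, 7.4 and 7.4.4 do not share one target.

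**Stronger readings that the documents do not support.** A reader might infer that the fallback misses the estimand whenever effects vary; the cancelling case above shows otherwise. A reader might infer that the trial's conclusion is read from this interval; the rule in 7.11 on whether the interval contains one only defines a tipping point for the missing-not-at-random analysis. A reader might infer a type I error problem; with a common risk ratio, including 1, the two targets coincide.

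**Conclusion.** The claim in SAP 7.4.4 that size weighting secures the participant-level effect is correct for the risk difference and wrong for the risk ratio as specified. This follows from the algebra and needs no assumption about the data.

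The practical size does depend on assumptions. For effects independent of baseline risk, mild variation (SD of log RR 0.2) shifts the risk ratio by about 2%, and the log-link alternative gains no coverage. From SD 0.3 upwards the shift is material. The direction is not fixed. The degree of variation is assumed throughout, and the Step 2 figures also assume log-normal risks unrelated to facility size.

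Given the remote trigger and the planned GEE, this is a worthwhile correction to a pre-specified fallback. It is not a threat to the main analysis.

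**What to change.** In SAP 7.4.4, for the primary-outcome fallback only, replace the linear regression on log proportions with one of these:

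1. A log-link regression of facility event counts in the post-randomisation period, with log(births) as offset, allocation, baseline adjustment and robust standard errors. The baseline proportion must enter in a form defined at zero events, for example untransformed, or as log((events + 0.5)/(births + 1)) as in the simulation above.
2. The ratio of the two adjusted size-weighted mean risks from the risk-difference regression already specified, with a delta-method or bootstrap confidence interval.

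Either targets the same ratio of mean risks as 7.4, agrees with the fallback risk difference, and keeps facilities with zero events.

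**Cost.** SAP wording and one changed command, with no new data. Under strong variation in effect (SD 0.5) the standard error of log RR is slightly larger, about 0.127 against 0.114, and in some scenarios coverage is a little below 95%. For option 1, precision also depends on how the baseline term is entered: in a check, the untransformed proportion gave somewhat larger standard errors than the log-proportion fallback. The form should therefore be fixed in advance.

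The fallback for secondary outcomes in SAP 7.5 is deliberately unweighted. That is a separate matter, and this change should not be carried over to it.
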